3.8 Procedural Exclusions

Procedurally excluded populations will include subjects who have enrolled in the study and start the procedure, but do not undergo a cardiac ablation procedure for the treatment of atrial fibrillation or if in the renal denervation arm of the study and do not have the EnligHTN™ Renal Denervation System enter his/her body, due to their anatomy, circumstances related to the procedure, or physician judgment. The reason for the procedural exclusion will be documented on the Termination CRF.

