4.3 Randomization Procedure

Using a 2:1 randomization scheme, each subject will be randomized to an atrial ablation procedure with concomitant renal denervation or an atrial ablation procedure alone.

Each subject will be randomized after the following is completed:

- Baseline evaluation
- Inclusion/Exclusion evaluation
- Subject signs study-specific consent form
- Cardiac ablation procedure for treatment of atrial fibrillation is complete.

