4.5 Renal Denervation Procedure

For patients randomized to receive the renal denervation procedure, the procedure should be completed per the institution's standard of care and the study device Instructions for Use.

Procedural data collected will include but is not limited to:

- EnligHTN™ Renal Denervation System device information
- Guiding catheter used manufacturer
- Number of arteries ablated
- Number of ablations performed
- Device settings
- Procedure time
- Ablation time
- Fluoroscopic time
- Volume of contrast media

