4.11 Clinical Investigation Termination

Each subject will be followed for 2 years post ablation procedure or until time of death, loss to follow up, withdrawal or clinical investigation termination. The clinical investigation will be complete after all follow-up visits are performed, all data is received by the Sponsor and the database is locked. The study will be closed when a final report is written on the conclusions and analysis of the data.

Participation in this clinical investigation is voluntary. Subjects are free to withdraw from the clinical investigation at any time without reason. However, subjects should be strongly encouraged to complete the protocol required follow up. Should a subject wish to withdraw prior to completing 60-month follow-up, the investigator should request the subject to come in for a final visit and a Termination CRF should be completed by the site and provided to the Sponsor.

At this visit the subject should undergo the following evaluations:

• Office Blood Pressure measurement

- Blood/Urine labs
- 12 Lead ECG

In a situation where a clinical investigation withdrawal is due to an adverse event the subject should be followed until resolution of that adverse event or determination that the subject's condition is stable. Upon withdrawal from the study, data will cease to be collected on Case Report Forms.

Subjects must be informed about their right to withdraw from the investigation at any time and for any reason without sanction, penalty or loss of benefits to which the subject is otherwise entitled and withdrawal from the investigation will not jeopardize their future medical care or relationship with the investigator. Subjects will be asked to specify the reason for the withdrawal, but have the right not to answer.

The investigator may decide to withdraw a subject from the investigation at any time. The subject's future care will not be influenced by a decision, voluntary or otherwise, to withdraw from the investigation. All reasonable efforts should be made to retain the subject in the clinical investigation until completion of the investigation.

Reasons for termination include, but are not limited to, the following:

- Subject did not meet the inclusion/exclusion criteria
- Subject requests to be withdrawn from the study
- Investigator withdraws subject from the study
- Subject lost to follow-up, defined as the following: a subject will be considered

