5.12.2 Investigation Conclusion

The investigation will be concluded when:

- A Close Out visit has been performed at each participating center AND
- The Final report has been provided by the sponsor

6 Risks and Benefits of the Clinical Investigation

Anticipated Adverse Events and Adverse Device Effects

Possible adverse events associated with the cardiac ablation procedure include, but are not limited to:

Cardiac Events:

- Abnormal ECG
- Angina (chest pain)
- Arrhythmia
- AV fistula
- Complete heart block
- Coronary artery injury
- Cardiac Perforation
- Cardiac Thromboembolism
- Myocardial infarction
- Obstruction/perforation/damage of the vascular system

- Death
- Dislodgement of implantable cardioverter defibrillator permanent pacing lead
- Endocarditis
- Exacerbation of pre-existing atrial fibrillation
- Heart Failure
- Hypotension heart block)
- Left atrial / esophageal fistula
- Pulmonary vein dissection
- Pulmonary vein stenosis

SJM CONFIDENTIAL AND PROPRIETARY

- Palpitation
- Pericardial effusion/cardiac tamponade
- Pericardial effusion without tamponade
- Pericarditis
- CHF exacerbation fluid overload
- Component damage to ICD or implantable pacemaker

- Pulmonary vein thrombus
- Temporary or complete heart block
- Unintended (in)complete AV, sinus node, heart block/damage
- Vessel wall/valvular damage or insufficiency
- Ventricular arrhythmia requiring defibrillation
- Bradycardia

Non-Cardiac Events:

- Air embolism
- Anesthesia reaction
- Cerebrovascular accident
- High creatinine phosphokinase (CPK)
- Infections
- Local hematomas / ecchymosis
- Laceration
- Phrenic nerve damage
- Pneumonia

- Pulmonary edema
- Pulmonary embolism
- Pulmonary hypertension
- Pleural effusion
- Pseudoaneurysm
- Respiratory depression
- Skin burns
- Syncope
- Transient ischemic attack
- Vasovagal reactions
- Vasovagal episodes

- Pneumothorax
- Vasospasm

Possible adverse events associated with the renal denervation procedure include, but are not limited to:

- Acute renal injury (renal infarction, renal hematoma)
- Renal vascular injury (renal artery dissection, renal artery thrombosis, renal artery stenosis)
- Collateral tissue injury
- Malignant or accelerated hypertension
- Symptomatic hypotension
- Access site complications (arteriovenous fistula, access site thrombosis, embolisation, pseudo-aneurysm, hematoma, limb ischemia, femoral nerve injury, or seroma)
- Disseminated intravascular coagulation

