7.3 Analysis Population

All patients who have signed a Patient Informed Consent (PIC) will be considered enrolled in the study. However, the Primary Analysis population will only include those patients that have signed a PIC, have undergone a cardiac ablation procedure for the treatment of atrial fibrillation, and, if in the renal denervation arm of the study, had the EnligHTN™ Renal Denervation System enter his/her body.

It is anticipated that there may be subjects who have been enrolled in the study but are not included in the Primary Analysis population, such as:

- Subjects who are enrolled but do not meet baseline inclusion or exclusion criteria before the procedure; these are considered the screen failure population.
- Procedurally excluded populations will include subjects who have enrolled in the study and start the procedure, but do not undergo a cardiac ablation procedure for the treatment of atrial fibrillation or if in the renal denervation arm of the study and do not have the EnligHTN™ Renal Denervation System enter his/her body, due to their anatomy, circumstances related to the procedure, or physician judgment.

Subjects who withdraw from the investigation will not be replaced in any analysis population.

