#### 2.3 Data Analysis and Reporting

Data analysis will be performed across all subjects based on Primary Analysis population unless otherwise specified.

The data collected will be presented using the appropriate summary statistics. Continuous data will be summarized using descriptive statistics (mean, number of observations, standard deviation, minimum and/or maximum values) and categorical data will be summarized using frequencies and percentages.

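### Denervation-arm subjects whom the EnligHTN system never enters drop out of that arm's MACE and peri-procedural rates after randomisation, and the protocol leaves their follow-up unclear

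*Protocol*

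**What the plan says.** **Timing.** Protocol 4.3 lists what must be done before a subject is randomised. The last item is "Cardiac ablation procedure for treatment of atrial fibrillation is complete".

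**Exclusion.** Protocol 3.8 defines procedural exclusion. It covers subjects who start the procedure but receive no AF ablation, and also subjects "if in the renal denervation arm of the study and do not have the EnligHTN™ Renal Denervation System enter his/her body", whether because of anatomy, procedural circumstances or physician judgment. It then says: "The reason for the procedural exclusion will be documented on the Termination CRF".

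**Analysis set.** Protocol 7.3 reads "However, the Primary Analysis population will only include those patients that have signed a PIC, have undergone a cardiac ablation procedure" and adds, for the denervation arm only, that the system must have entered the body. SAP 2.2 repeats this. SAP 2.3 makes the set the default: "Data analysis will be performed across all subjects based on Primary Analysis population unless otherwise specified". Protocol 7.4 has the same rule.

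**Safety rates.** SAP 2.5.1 (7-day MACE and 30-day peri-procedural events) and SAP 2.5.2 (MACE at 6 months, 1 year and 2 years) name no wider set. SAP 2.5.2 also defines an overall renal vascular safety rate, whose denominator is all subjects randomised to denervation.

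**Follow-up.** Protocol 4.11 says: "Each subject will be followed for 2 years post ablation procedure or until time of death, loss to follow up, withdrawal or clinical investigation termination". Procedural exclusion is not among those end points. Protocol 5.7.8 applies safety surveillance to all enrolled subjects.

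**The concern.** A denervation subject who is excluded in this way has already been ablated and randomised. Removing that subject is a post-randomisation exclusion that can happen in one arm only. A control subject with the same renal anatomy stays in every rate.

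The excluded subjects may also have been exposed to part of the renal procedure. Protocol section 6 lists among its risks "Access site complications (arteriovenous fistula, access site thrombosis, embolisation, pseudo-aneurysm, hematoma, limb ischemia, femoral nerve injury, or seroma", and some of these could follow arterial access even if the device is never introduced. A safety summary for a strategy of adding denervation should count harm from attempts that fail.

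The cut-off is also uneven. Protocol 3.13.2 counts the optional EnligHTN guiding catheter as part of the system, while 4.5 collects "Guiding catheter used manufacturer", which implies that other makes may be used. A guide-related injury could then be counted or not according to the brand of guide.

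Finally, the reason for exclusion goes on the form used when participation ends. If sites read that as an instruction to exit the subject, the data needed for an all-randomised analysis would not exist.

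**Working it through.** **1. The plan's own figure.** SAP 2.2 gives 75 subjects with at least 50, or two thirds, receiving both procedures: 75 × 2/3 = 50. This reproduces. With the protocol's 100 subjects, 100 × 2/3 = 66.7, so 67 is used below as the upper case. No power calculation exists to reproduce; the study is descriptive.

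**2. Which filter acts after randomisation.** The requirement of an AF ablation applies to both arms, but under 4.3 every randomised subject has already met it. The requirement that the system entered the body applies only to the denervation arm and can only fail after allocation. So the only post-randomisation filter is in that arm.

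**3. Which rates are affected.**

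| Rate | Set or denominator | Excluded subject's event counted? |
|---|---|---|
| 7-day MACE (SAP 2.5.1) | default set, followed 7 days or had event | No |
| 30-day peri-procedural (SAP 2.5.1) | default set, followed 30 days or had event | No |
| MACE at 6 months, 1 and 2 years (SAP 2.5.2) | default set, followed to time point or had event | No |
| Overall renal vascular safety (SAP 2.5.2) | all randomised to denervation | Yes, if observed |

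**4. Size.** The documents give no exclusion or event counts, so all counts here are assumptions: N = 50 or 67 randomised to denervation; k = 1, 3 or 5 never entered; c = 0, 1 or 2 of those with an event (c ≤ k); b = 0 or 2 events among the rest.

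Reported rate = b/(N − k). All-randomised rate = (b + c)/N.

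| N | k | c | b | Reported | All randomised | Difference (points) |
|---|---|---|---|---|---|---|
| 50 | 3 | 1 | 0 | 0/47 = 0.0% | 1/50 = 2.0% | 2.0 |
| 50 | 3 | 2 | 0 | 0/47 = 0.0% | 2/50 = 4.0% | 4.0 |
| 50 | 3 | 2 | 2 | 2/47 = 4.3% | 4/50 = 8.0% | 3.7 |
| 67 | 5 | 1 | 2 | 2/62 = 3.2% | 3/67 = 4.5% | 1.3 |
| 67 | 5 | 2 | 2 | 2/62 = 3.2% | 4/67 = 6.0% | 2.7 |
| 50 | 5 | 0 | 2 | 2/45 = 4.4% | 2/50 = 4.0% | −0.4 |

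Over the whole grid, one omitted event lowers the reported rate by 1.3 to 2.0 points and two by 2.7 to 4.0. With none omitted, exclusion leaves the rate unchanged or raises it by up to 0.4.

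Protocol 3.11 does not count excluded subjects toward the 50. Reaching 50 treated with 3 excluded therefore needs 53 randomised. One omitted event and none elsewhere then gives 0/50 = 0.0% against 1/53 = 1.9%, inside the same range.

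**5. Follow-up passages side by side.**
- Pointing to exit: 4.11 uses the Termination CRF at a final visit on withdrawal, 5.8.1 asks for it because death ends participation, and the Withdrawal/Termination row in Tables 1 and 2 opens at the Procedure column.
- Pointing to continued follow-up: 4.11 plans 2 years for each subject without naming procedural exclusion as an end point, and stops CRF data only on withdrawal. Section 5.7.8 covers all enrolled subjects until the last visit, death or the end of participation.

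**6. Why the two parts are linked.** The SAP 2.5.1 denominators keep subjects who were followed long enough or had an event. Widening the set alone would not be enough if event-free excluded subjects exit early. With N = 50, k = 3, c = 1, b = 2 and the other two excluded subjects gone before day 30, the rate becomes 3/48 = 6.25% rather than 3/50 = 6.0%.

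**The case against.** A reader might infer that follow-up ends at procedural exclusion. No passage says so. Section 3.8 only says where the reason is recorded, without timing; the termination reasons in 4.11 are not exhaustive and include completing the study; and nothing calls procedural exclusion a withdrawal. Early exit is plausible but not established, so a loss of 24 months of data cannot be claimed.

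A reader might also infer that these subjects vanish from all of the arm's safety rates. They do not: overall renal vascular safety is already taken over everyone randomised to denervation. That rate does not cover MACE or the 30-day peri-procedural rate, however, and if subjects did exit, it would carry them in the denominator with no later observation.

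It can be argued that SAP 2.5.1, by giving peri-procedural rates per randomisation arm and stating its own denominator, has specified something other than the default. That wording sets the grouping and the follow-up needed; it does not name a wider population. SAP 2.2's promise to use all available data concerns withdrawn subjects, and the As Treated analysis in SAP 2.6 is optional and undefined.

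The direction of bias is also conditional. If no excluded subject has an event, the reported rate is slightly too high, not too low. The guide-brand point is narrow too: it concerns attempts stopped at access or with another maker's guide, and the documents do not describe the order of steps. These limits stand. The one-arm exclusion does not depend on them.

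**Conclusion.** The point holds for the 7-day MACE, 30-day peri-procedural and later MACE rates. As written, the plan removes from these, in the denervation arm only, any randomised subject the system did not enter, together with that subject's events. The documents do not support saying that follow-up stops, that every safety rate is affected, or that safety is understated in all cases. Follow-up after exclusion is ambiguous, and the passages must be reconciled.

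The likely effect is small in counts but visible in an arm of about 50: roughly 1.3 to 4.0 points if one or two events are omitted, and at most about 0.4 points the other way if none is. These figures rest wholly on the assumed counts. With no hypothesis test planned, the consequence is a possibly biased descriptive safety comparison, not an invalid test. It should be corrected because the correction is cheap and the follow-up data may not be recoverable later.

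**What to change.** **Protocol 3.8.** Record a procedural exclusion that occurs after randomisation on the Procedure CRF. State that the subject stays in scheduled follow-up under 4.10 and in safety reporting under 5.7.8. Reserve the Termination CRF for actual study exit, and align 4.11 with this.

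**SAP 2.5.1 and 2.5.2.** Compute the MACE and peri-procedural rates by arm on all randomised subjects, in line with the denominator already used for overall renal vascular safety. Show the device-entered rate beside it. Limiting the denominator to subjects with attempted renal access would not be enough: it would still drop those excluded earlier for anatomy or physician judgment, and the arms would remain non-comparable.

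**Cost.** Some protocol wording, one CRF instruction, one extra denominator and follow-up visits for a few subjects. The denervation-arm safety figures may look slightly less favourable.

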3.9 Expected duration of the Investigation

The expected duration of the investigation from first enrollment until final follow-up is approximately three (3) years.

3.10 Expected duration of each subject's participation

The expected duration of each subject enrolled in the clinical investigation is two (2) years.

3.11 Number of subjects required to be included in the Investigation

Using a 2:1 randomization, a total of up to 100 patients will be enrolled in the investigation and will undergo the cardiac ablation procedure. Enough subjects will be enrolled to have at least 50 subjects undergo the concomitant atrial fibrillation ablation and renal denervation procedure in the investigation. Procedurally excluded subjects will not count towards the expected number of treated subjects.

3.12 Estimated time needed to select this subject population

The estimated time needed to enroll the required number of subjects is approximately 8 months.

3.13 Devices Used

3.13.1 Atrial Fibrillation Ablation Procedure

The market approved St. Jude Medical devices to be used in this investigation include:

Safire BLU™ Duo or Therapy Cool Path Duo Irrigated Ablation Catheter or Therapy Cool Flex Irrigated Ablation Catheter
EnSite Velocity System
Agilis NxT Guiding Introducer

3.13.1.1 Atrial Fibrillation Ablation Catheter

Either the Safire BLU™ Duo ablation catheter, the Therapy™ Cool Path™ Duo ablation catheter or the Therapy™ Cool Flex™ ablation catheter will be used to perform the atrial ablation procedure. These catheters are sterile, single use 7F catheters that are constructed of thermoplastic elastomer material and four noble metal electrodes. These catheters have a through-lumen connected to open conduits at the 4mm tip electrode for heparinized saline irrigation during the ablation procedure. The tip curvature may be manipulated by the control mechanism located in the handle at the proximal end of the catheter.

3.13.1.2 3D Mapping System

A 3D electroanatomical mapping system will be used per the center's standard workflow to support the atrial ablation procedure. In particular, the EnSite Velocity™ Cardiac Mapping System may be used. This is a catheter navigation and mapping system capable of displaying the three dimensional (3D) position of conventional electrophysiology catheters, as well as displaying cardiac electrical activity as waveform traces and as dynamic 3-D isopotential maps of the cardiac chamber. The contoured surfaces of these three-dimensional maps are based on the anatomy of the patient's own cardiac chamber.

3.13.1.3 Guiding Introducer

An Agilis NxT Steerable Introducer will be used to support the left atrial ablation procedure. It is anticipated that it will be used to help guide and maneuver the irrigated ablation catheter as per the center's standard of care. The Agilis NxT is indicated for introducing various cardiovascular catheters into the heart, including the left side of the heart through the interatrial septum

3.13.2 Renal Denervation Procedure

The EnligHTN[™] Renal Denervation System is designed to deliver radiofrequency (RF) energy to the renal nerves to achieve targeted denervation. The system consists of the EnligHTN[™] RF Ablation Generator (generator), the EnligHTN[™] Renal Artery Ablation Catheter (ablation catheter), and the EnligHTN[™] Guiding Catheter (optional).

The market approved St. Jude Medical devices to be used in this investigation include:

EnligHTN™ Renal Artery Ablation Catheter EnligHTN™ RF Generator EnligHTN™ Guiding Catheter (optional)

3.13.2.1 EnligHTN™ Renal Artery Ablation Catheter

The EnligHTN™ Renal Artery Ablation Catheter is a single use device that has an expandable electrode basket with four Platinum-Iridium (Pt-Ir) ablation electrodes. The electrodes deliver low-level radiofrequency energy to the renal arteries through a percutaneous vascular access site. The distal segment of the ablation catheter is deflectable to assist in proper basket positioning. The handle is used to actuate the expansion and relaxation of the basket, and to

Clinical Investigational Plan: RDN + AF

[©] 2013 – St. Jude Medical Cardiovascular Division: All rights reserved. No portion of this work may be reproduced in whole or in part without the express written permission of St. Jude Medical Cardiovascular Division.

actuate the deflection of the ablation catheter at the distal end. The ablation electrodes and the tip are radiopaque to provide visualization under fluoroscopy.

3.13.2.2 EnligHTN™ RF Ablation Generator

The EnligHTN™ RF Ablation Generator delivers RF energy to the EnligHTN Renal Artery Ablation Catheter using a proprietary algorithm developed to produce a consistent, transmural ablation pattern during the renal denervation procedure.

3.13.2.3 EnligHTN™ Guiding Catheter (optional)

The EnligHTN™ Guiding Catheter system is comprised of two (2) components: a guiding catheter and a dilator. The guiding catheter is constructed of three (3) components: a polytetrafluoroethylene (PTFE) liner, a stainless steel braid, and a multi durometer polymer jacket. The proximal end of the catheter terminates in a hemostasis hub and a hemostasis valve. An extension tube and 3-way stopcock valve is attached to the sideport of the hemostasis hub. The distal end of the catheter terminates in a renal curve with a radiopaque marker embedded in the polymer jacket approximately 2 mm from the catheter tip. The dilator is a polymer tube with an inside diameter sized for guidewire clearance. The proximal end terminates in a snap fitting to mate with the guiding catheter hemostasis hub. The distal end is tapered to facilitate insertion through an introducer sheath.

3.14 Intended Use

The cardiac ablation catheter is indicated for diagnostic and therapeutic use. It has the ability to record intracardiac electrograms and can be utilized for cardiac stimulation during diagnostic electrophysiologic studies/evaluation, as well as for the delivery of RF energy for the treatment of arrhythmias.

The renal denervation ablation catheter is indicated for use in renal denervation procedures for the treatment of hypertension.

4 Procedures

Table 2: Data/CRF Collection

Study Activity	Enrollment / Baseline*	Procedure ≤30 days after Enrollment	Discharge <72 hrs	1M ±7d	3M ±10d	6M ±14d)	12M ±21d	24M ±60d
Consent Process	Х							
Inclusion/Exclusion	Х							
Medical and Cardiovascular History	Х							
12-Lead ECG	Х	X	Х	Х	Х	Х	Х	Х
Office Blood Pressure	Х			Х	Х	Х	Х	Х
Physical Assessment	Х			Х	Х	Х	Х	Х
24-h Ambulatory Blood Pressure	X-performed w/in 90 days prior to procedure					Х	Х	х
Discharge Blood Pressure			Xp					
Echocardiography (TTE)	Х			Х		Х	Х	Х
NYHA Assessment	Х			Х		Х	Х	Х
Serum creatinine	Х					X ^t	X ^t	X ^t
Estimated GFR	X					X ^t	X ^t	X ^t
Hemoglobin A1c	Х					X ^t		
Fasting Glucose	Х					X ^t		
Fasting Insulin	Х					X ^t		
Urine albumin-to- creatinine ratio	Х					X ^t		X ^t
Quality of Life Assessment (EQ-5D 5L & AFEQT)	Х			Х		Х	Х	Х
Renal Artery Anatomy Evaluation	X					X ^t	X ^t	
Pregnancy Test (urine / blood)	Х							
Renal Denervation Procedure		X ^t						
Cardiac Ablation Procedure		Х						

SJM CONFIDENTIAL AND PROPRIETARY

Clinical Investigational Plan: RDN + AF

[©] 2013 – St. Jude Medical Cardiovascular Division: All rights reserved. No portion of this work may be reproduced in whole or in part without the express written permission of St. Jude Medical Cardiovascular Division.

7 Day Holter or Event Monitor			Х		Х	Х	Х	Х
Medications	X	Х	Х	Х	Х	Х	Х	Х
Adverse Event	**	**	**	**	**	**	**	**
CIP Deviation	**	**	**	**	**	**	**	**
Withdrawal/ Termination		**	**	**	**	**	**	**

- (*) Baseline tests and procedures must be performed within 90 days of Enrollment.
- (**) as applicable
- (b) monitored every 4 hours post procedure until discharge, or for a maximum of 24 hours
- (t) only applicable to patients who are in the renal denervation randomization group

